11.3.5 Medical History and Concomitant Diseases

Medical history is defined as any condition that started and ended prior to Screening. Medical history will be coded using Medical Dictionary for Regulatory Activities (MedDRA) version 16.0 and listed separately by sequence, System Organ Class (SOC) and Preferred Term (PT) within SOC.

Concomitant disease is defined as any condition diagnosed at Screening or was ongoing at Screening. Concomitant disease will be coded using MedDRA version 16.0 and listed separately by sequence, SOC and PT within SOC.

Philip Morris Products S.A. Protocol ZRHR-PK-01-EU Statistical Analysis Plan Final v 3.0 / 08 May 2014 Confidential Page 41 of 72

Partial dates will not be imputed, but assumptions will be made as follows to assign to either medical history or concomitant diseases:

Date information	Assign as
Missing stop date	Concomitant
	disease
Partial date, e.gMay2012, or2011. If month/year	Concomitant
is the same as, or later than the month and/or year of	disease
Screening.	
Partial date, e.gMay2012, or2011. If month	Medical history
and/or year is earlier than the month and/or year of	
Screening.	

The data will be presented in the below outputs:

TFL number	Title
TABLES	
15.2.1.6	Summary of Medical History – Safety Population
15.2.1.7	Summary of Concomitant Diseases – Safety Population
LISTINGS	
15.3.1.10	Listing of Medical History and Concomitant Disease

11.3.6 Other Data

Other data collected at Screening and/or Admission will be listed by sequence and subject. These data are as follows:

- Cotinine urine test
- Urine pregnancy test
- Chest x-ray
- Urine drug screen
- Serology
- Alcohol breath test
- Prior medication
- Product Test and Demonstration
- Identification of NNS brand
- Willingness to use THS 2.2 and NNS products

Willingess and ability to use the products will also be summarized.

TFL number	Title
TABLES	
15.2.1.1	Summary of Subject Disposition –All Screened Subjects

Philip Morris Products S.A. Protocol ZRHR-PK-01-EU Statistical Analysis Plan Final v 3.0 / 08 May 2014 Confidential Page 42 of 72

TFL number	Title
LISTINGS	
15.3.1.5	Listing of Product Test, Willingness to Use the Product, Willingness to
	Quit Smoking, Readiness to Accept Smoking Interruption
15.3.1.6	Listing of Safety Laboratory Entry Criteria
15.3.6.3	Listing of Prior and Concomitant Medication

11.4 Measurements of Product Compliance

Levels of CO in exhaled breath will be measured to evaluate the exposure to CO (see Section 11.6.2.2.1 "Exhaled CO and COHb"), and to monitor compliance during the following study days (see Section 6.3.3 "Compliance to Product Allocation"):

- Wash-out on Day 0 and Day 2.
- Single use Day 1 and Day 3 for subjects exposed to NNS.

CO data will be listed and summarized by sequence for all study days and timepoints as continuous variable and with the categorization ≤ 10 ppm and >10 ppm.

Values above 10 ppm will be highlighted in listings and be considered as non compliance if such values are observed prior to first product use on the single use days for all exposures and throughout the single use days for NNS exposure. During the washout days values above 10 ppm will be considered non-compliance on Day 2, but will be expected on Day 0 because smoking is ad libitum during Day -1. CO data leading to exclusion of subjects from the analysis will be evaluated during the pre-analysis blind data review.

Number and percentage of subjects considered as non compliant during the study will be tabulated by sequence and study days for the Randomized population

TFL number	Title
TABLES	
15.2.4.10.1	Descriptive Statistics of Exhaled CO (ppm) During Single Use
	Continuous Measurements- PK Population
15.2.4.10.1.1	Descriptive Statistics of Exhaled CO (ppm) During Single Use by Sex –
	PK Population
15.2.4.10.1.2	Descriptive Statistics of Exhaled CO (ppm) During Single Use by
	Nicotine Level – PK Population
15.2.4.10.2	Descriptive Statistics of Exhaled CO (ppm) During Single Use
	Categorical Measurements- PK Population
15.2.4.11.1	Descriptive Statistics of Exhaled CO (ppm) During Days -1, 0, 2 and 4
	Continuous Measurements- PK Population
15.2.4.11.1.1	Descriptive Statistics of Exhaled CO (ppm) During Days -1, 0, 2 and 4
	by Sex – PK Population

Philip Morris Products S.A.	Statistical Analysis Plan	Confidential
Protocol ZRHR-PK-01-EU	Final v 3.0 / 08 May 2014	Page 43 of 72

TFL number	Title
15.2.4.11.1.2	Descriptive Statistics of Exhaled CO (ppm) During Days -1, 0, 2 and 4
	by Nicotine Level – PK Population
15.2.4.11.2	Descriptive Statistics of Exhaled CO (ppm) During Days -1, 0, 2 and 4
	Categorical Measurements- PK Population
15.2.5.1	Descriptive Statistics of Compliance– Randomized Population
LISTINGS	
15.3.3.5	Listing of Exhaled Breath CO (ppm) and Measurement Times

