5.2 Secondary Objectives and Endpoints

- 1. To determine if C_{max} and $AUC_{(0-last)}$ of the THS 2.2 are higher relative to nicotine nasal spray (NNS) following single use of the THS 2.2 and NNS. Endpoints:
 - C_{max} [NNS and THS 2.2, Group-2]
 - AUC_(0-last) [NNS and THS 2.2, Group-2]
- 2. To evaluate the difference on nicotine pharmacokinetic (PK) absorption parameters (AUC from start of product use extrapolated to time of last quantifiable concentration to infinity $[AUC_{(0-\infty)}]$ and partial AUC, where t' is the subject-specific time of maximum nicotine concentration following single use of the CC or NNS product $[AUC_{(0-t')}]$ between the THS 2.2 and CC, as well as the THS 2.2 and NNS.

Endpoints:

- AUC_(0-∞).
- Partial AUC_(0-t').
- 3. To evaluate the time to the maximum concentration (t_{max}) of nicotine for the THS 2.2 as compared to CC and to determine if the tmax for THS 2.2 is shorter as compared to NNS.

Endpoint:

- t_{max} .
- 4. To describe the terminal half-life $(t_{1/2})$ of nicotine for the THS 2.2, CC, and NNS. Endpoint:
 - t_{1/2}.

Philip Morris Products S.A. Protocol ZRHR-PK-01-EU

Statistical Analysis Plan Final v 3.0 / 08 May 2014 Confidential Page 12 of 72

5. To describe the differences on urge-to-smoke over time between the THS 2.2 and CC, as well as between the THS 2.2 and NNS.

Endpoints:

Urge-to-smoke as measured with the Questionnaire of Smoking Urges brief (QSU-brief) (Cox et al, 2001).

- Total score.
- Factor-1.
- Factor-2.

6. To describe product evaluation in the THS 2.2 and CC users.

Endpoints:

Product evaluation as measured with the Modified Cigarette Evaluation Questionnaire (MCEQ) (Cappelleri et al, 2007) [CC and THS 2.2, in Group-1]

- Smoking Satisfaction subscale.
- Enjoyment of Respiratory Tract Sensation subscale.
- Psychological Reward subscale.
- Aversion subscale.
- Craving Reduction subscale.
- To describe the levels of carbon monoxide (CO) exposure for the THS 2.2, as compared to CC and NNS users.
 Endpoints:

Endpoints:

- Levels of exhaled CO.
- Carboxyhemoglobin (COHb) in blood.
- 8. To monitor the safety during the study. Endpoints:
 - Incidence of adverse events (AEs)/serious adverse events (SAEs) and device events, including THS 2.2 malfunction/misuse.
 - Respiratory symptoms: cough assessment by visual analogue and Likert scales and one open question.
 - Vital signs (systolic and diastolic blood pressure, pulse rate, respiratory rate).
 - Spirometry.

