6.3.3 Compliance to Product Allocation

Compliance will be ensured by strict distribution of the products (product by product) and collection of used Tobacco Sticks, the CC butts and/or the NNS after each use. This information will be documented in appropriate logs.

In addition, in subjects using NNS, the compliance will be chemically verified using exhaled CO breath. The cut-off point for the CO breath test value to distinguish tobacco use vs. no tobacco use will be 10 ppm (Bennowitz et al, 2002).

Furthermore, the CO breath test will be considered as a measure of compliance during the wash-out days for all subjects.

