10.3.1 Major Protocol Deviations

Subjects with major protocol deviations will be identified (at a population level) to determine whether they will be excluded from any of the analysis populations. The following have been identified as the major protocol deviations.

The categories for the major deviations will include, but are not limited to the deviations presented in Table 10.

Table 10: Definition of Major Protocol Deviations

Category	Description
Violation	Violation of inclusion/exclusion criteria
Mis-randomization	Being administered the wrong product according to the randomization schedule
Mis-use of product	 Use of any nicotine or tobacco–containing product other than the assigned product during the exposure period, or use of any nicotine tobacco-containing product during wash-out days (e.g. see Section 11.4 "Measurements of Product Compliance"). Use of assigned product inconsistent with the labeled use (e.g., number of sprays of the NNS is not 2)
Concomitant medication	Use of any drugs which are known to affect CYP2A6 activity

Among the above criteria, violations of inclusion criteria 5 to 7, or of the exclusion criteria 1, 3 to 16, and 18 will be assessed for their impact on the PK population and evaluated during the pre-analysis data review meeting (Section 6.3.2 "Methods of Assigning Subjects to Treatment Sequences").

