11.6.2.1.2 THS 2.2 vs NNS

The following analyses will be conducted in only Group-2 PK population:

• The secondary analysis of C_{max}, AUC_(0-last), AUC_(0-∞), AUC_(0-t') and t_{1/2} parameters will be performed using the same ANOVA model as used for the primary analysis. (Section 11.6.1 "Primary Analyses").

Only subjects in the Group-2 PK population who provide evaluable data for both the THS 2.2 and CC products will be included in the analyses.

Philip Morris Products S.A. Protocol ZRHR-PK-01-EU Statistical Analysis Plan Final v 3.0 / 08 May 2014 Confidential Page 47 of 72

The analysis of C_{max} and $AUC_{(0-last)}$ will test if the lower bound of the 95% CI for the ratio (THS 2.2 : NNS) is > 1.0 at the 0.025 level of significance in order to determine if the rate and the amount of nicotine absorbed of the THS 2.2 is higher relative to NNS. This approach will be used to test the following hypothesis for both C_{max} and $AUC_{(0-last)}$ parameters:

 $H_0: X_{THS} / X_{NNS} = 1.0 \\ H_A: X_{THS} / X_{NNS} > 1.0$

where X_{THS} and X_{NNS} are the adjusted geometrical means of THS 2.2 and NNS, respectively. H₀ is rejected with a type I error $\alpha = 0.025$ (one-sided test).

• To test if the time to the maximum nicotine concentration in THS 2.2 is shorter than in NNS the following hypothesis will be evaluated:

H₀: $X_{THS} - X_{NNS} = 0$ H_A: $X_{THS} - X_{NNS} < 0$

where X_{THS} and X_{NNS} are the median values of the THS 2.2 and NNS, respectively. t_{max} will be analysed on the original scale using the Wilcoxon Signed-Rank Test with a type I error $\alpha = 0.025$ (one-sided test), as values are ordinal/discrete, and the assumption of normality may be questionable.

The analysis of t_{max} will be performed by calculating the difference for each subject (THS 2.2 - NNS) and obtaining the Hodges-Lehmann 95% CI estimates (**Hodges and Lehmann, 1963**). The median t_{max} for each product and the median difference between the products along with the 95% CI will be presented.

Supportive analysis will be performed as described in Section 11.6.3 "Supportive/Sensitivity Analysis".

The data will be presented in the below outputs:

TFL number	Title
TABLES	
15.2.4.2	Analysis of Pharmacokinetic Parameters of Nicotine – Group-2 PK
	Population

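### In Group-2, post-use exhaled CO above 10 ppm counts as non-compliance on NNS days but not on THS 2.2 days, so exclusions based on it can favour the THS 2.2 > NNS alternative

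*SAP*

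**What the plan says.** SAP Section 6.3.3 says that "in subjects using NNS, the compliance will be chemically verified using exhaled CO breath" and explains the threshold: "The cut-off point for the CO breath test value to distinguish tobacco use vs. no tobacco use will be 10 ppm". Section 11.4 turns this into a rule. On single use days a value above 10 ppm is non-compliance when seen "prior to first product use on the single use days for all exposures and throughout the single use days for NNS exposure". For wash-out, "During the washout days values above 10 ppm will be considered non-compliance on Day 2", whichever product comes next. On Day 0 such values are expected.

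The consequence is left to review: "CO data leading to exclusion of subjects from the analysis will be evaluated during the pre-analysis blind data review". Table 10 in Section 10.3.1 lists "Use of any nicotine or tobacco–containing product other than the assigned product during the exposure period" as a major deviation and refers to Section 11.4 as an example. Under Sections 10.1 and 10.3, a major deviation removes a subject from a PK population only if it is judged to affect evaluability.

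For Group-2, Section 11.6.2.1.2 tests C_max and AUC(0-last) one-sided at 0.025 to "determine if the rate and the amount of nicotine absorbed of the THS 2.2 is higher relative to NNS". Section 5.2 also has the objective "To describe the levels of carbon monoxide (CO) exposure for the THS 2.2, as compared to CC and NNS users". Under Section 10 the CO endpoints use the PK populations, and under Section 11.6.2.2.1 the model uses the post-T0 assessments.

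**The concern.** The same four breath tests are taken on both single use days (Table 12), but after T0 only the NNS day can produce a CO-based finding of non-compliance. The two kinds of extra smoking move the ratio in opposite directions:

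- on the NNS day, extra nicotine raises the denominator and lowers THS 2.2:NNS, and post-use CO can flag it;
- on the THS 2.2 day, extra nicotine raises the numerator and the ratio, and post-use CO does not flag it.

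Where CO is the only evidence, exclusion therefore removes cases that work against the tested alternative and keeps those that work for it. The comparison was planned with 18 subjects, so one or two exclusions are visible in the estimate.

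A second effect follows for the CO endpoint. Exhaled CO after T0 is an outcome of the THS 2.2 vs NNS comparison, and excluding subjects because that outcome was high under NNS selects on the outcome under one product.

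**Working it through.** **The plan's own figure.** Inputs from SAP Section 8: within-subject CV 36% (C_max) and 21% (AUC(0-last)), C_max ratio 1.55, 90% power, 10% dropout, 18 subjects.

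- SD of the paired log difference for C_max: √2 × √ln(1 + 0.36²) = √2 × 0.349 = 0.494.
- Effect: ln 1.55 = 0.438. A paired t-test at one-sided 0.025 has 89.1% power with 15 completers and 91.2% with 16.
- 16 / 0.9 = 17.8, rounded up to 18. The SAP figure is reproduced, and this point does not alter it.

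**One case on each day.** Assume 16 completers, a true AUC ratio of 1, and extra use that doubles that day's AUC. The THS 2.2-day case shifts its log ratio by +ln 2 = +0.693, the NNS-day case by −0.693.

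- Keep both: (0.693 − 0.693) / 16 = 0, no bias.
- Exclude both: no bias.
- Exclude only the NNS-day case: 0.693 / 15 = 0.046, a ratio of 1.047 (+4.7%).

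**Rates instead of single cases.** The SAP gives no rate of extra use, so the following are assumptions: a share p of subjects uses extra product on each day independently, it multiplies that day's exposure by f, CO always detects it, every flag leads to exclusion, and 16 complete. The SD of the log AUC difference is √2 × √ln(1 + 0.21²) = 0.294. With NNS-day-only exclusion the expected log bias is p × ln f; for example 0.10 × 0.693 = 0.069, a ratio of 1.07. Simulation with a true ratio of 1 (40,000 trials per setting) gave:

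| Parameter, f | p = 5% | p = 10% | p = 20% |
|---|---|---|---|
| AUC, f = 2 | 1.04; 4.8% | 1.07; 7.7% | 1.15; 16.6% |
| AUC, f = 1.5 | 1.02; 3.9% | 1.04; 6.1% | 1.08; 11.1% |
| C_max, f = 1.25 | 1.01; 2.9% | 1.02; 3.5% | 1.05; 4.7% |

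Each cell shows the estimated ratio and the one-sided error. With 50% detection, f = 2 and p = 10%, the figures are 1.03 and 4.4%. With no exclusion, or with exclusion for either day, the ratio stays at 1.00 and the error at 2.4% to 2.6%.

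**C_max can behave differently.** Suppose the extra product is used well after the first peak has fallen and gives a peak like that of THS 2.2. C_max on the THS 2.2 day then hardly moves. If the true C_max ratio is 1.55, C_max on the NNS day rises by about ln 1.55 = 0.44. With one case on each day, keeping both gives −0.44 / 16 = −0.027 (about −2.7%), while dropping the NNS-day case gives about 0. In this scenario the planned rule removes bias.

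**The CO endpoint.** No arithmetic is needed. If subjects with post-T0 CO above 10 ppm under NNS are excluded, the remaining NNS-day values lie at or below 10 ppm, while THS 2.2-day values have no such limit. Both periods of an excluded subject are lost.

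**The case against.** The best defence is that the asymmetry has a reason. Section 6.3.3 presents 10 ppm as separating tobacco from no tobacco. NNS contains none, so a high reading on an NNS day points to another product. THS 2.2 uses a Tobacco Stick, and the SAP gives no basis for reading the same value after its use as misconduct. This stands as an explanation of the rule, and it is why a THS 2.2-day reading should prompt review and not count as proof. It does not remove the directional effect. T0 lies between 06:00 and 09:00 and the first post-use breath test is no earlier than 12:00, at least three hours later, and the SAP gives no CO figure for a single stick.

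A reader might infer that evidence of extra smoking can remove a subject only when it lowers the ratio. The SAP does not support that. Pre-T0 CO and Day 2 CO apply whatever the product. Used sticks, butts and sprays are collected and logged, use of more than one stick is tabulated (Section 11.5), and Table 10 covers every exposure period. Only the post-T0 CO trigger is one-sided.

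A reader might also infer that the bias and the truncation of CO are built in. They are conditional, because exclusion follows review. That safeguard is limited: no CO exclusion criterion is fixed in advance, and the rule needs to know the product while Section 6.3.2 describes a listings review without access to the sequence.

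Finally, the comparison is secondary, the CO objective is descriptive, and Section 11.1.7 says no claims rest on individual tests. All of this limits the stakes.

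**Conclusion.** The point holds for Group-2 and for post-T0 CO evidence only. If subjects flagged solely by such a value on the NNS day are excluded, the selection can move the secondary THS 2.2:NNS AUC(0-last) ratio toward the tested alternative. It can do the same for C_max where extra use alters the peak on both days, though late use may leave C_max unbiased or better off under the planned rule. The exclusion also selects on exhaled CO under one product.

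The size is unknown. The figures above rest on assumed misuse rates, assumed effects on exposure and, mostly, perfect detection with every flag leading to exclusion. Confinement and product-by-product distribution should keep events few, so the real effect is probably small. The primary THS 2.2:CC analysis is not touched, because neither of its products has a post-use CO rule. It is still worth correcting before the data review, because the direction favours the hypothesis and the correction is cheap.

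**What to change.** In SAP Section 11.4, with matching wording in 6.3.3, and for Group-2 only:

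- send post-T0 exhaled CO above 10 ppm on either single use day to the pre-analysis review, under one exclusion criterion written down beforehand;
- report the Group-2 PK, exhaled CO and COHb analyses with and without subjects whose only evidence of non-compliance is a post-T0 CO value.

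Leave Group-1 without a post-use CO rule. Flagging THS 2.2 days there while CC days stay unflagged would create a new one-sided rule in the primary comparison, acting against THS 2.2:CC.

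The cost is a wording change, one programming condition and one repeated set of Group-2 outputs, with no new data. The small downside is that, because THS 2.2 is a tobacco product, a compliant subject could be flagged for review. The with/without reporting covers this. Keeping flagged subjects in the CO analyses is itself a trade-off, since some may truly have smoked, which is why both versions should be shown.

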11.5 Extent of Exposure (Product Consumption)

Details of the product test prior to enrollment and of product use after randomization will be listed by sequence for the Safety population.

The number and percentage of subjects who smoked 1, 2, or 3 (categories of 0 and >3 will be included if applicable) THS Tobacco Stick at admission will be tabulated; together with the number and percentage of subjects who performed the NNS product trial with 2 number of sprays (categories of 0, 1, >2 will be included if applicable).

The number and percentage of subjects who smoked 0 or 1 (category >1 will be included if applicable) THS Tobacco Stick, or CC during single use days (Day 1 or Day 3) will be tabulated by sequence; together with the number and percentage of subjects who performed the single use day of the NNS product with 0 or 2 number of sprays (categories of 1, >2 will be included if applicable).

The data will be presented in the below outputs:

TFL number	Title
TABLES	
15.2.2.1	Descriptive Statistics of Product Use - Safety Population
LISTINGS	
15.3.2.1	Listing of Product Usage
15.3.2.2	Listing of Cigarette Butt and Tobacco Stick Collection Data

Philip Morris Products S.A. Protocol ZRHR-PK-01-EU Statistical Analysis Plan Final v 3.0 / 08 May 2014 Confidential Page 45 of 72

11.6.2 Secondary Analyses

11.6.2.1 Pharmacokinetics

The secondary PK parameters from Group-1 PK population $(AUC_{(0-t')}, AUC_{(0-\infty)}, %AUC_{extrap}, t_{last}, t_{max}, \lambda_z \text{ and } t_{1/2})$ and the PK parameters from Group-2 PK population $(C_{max}, AUC_{(0-last)}, AUC_{(0-t')}, AUC_{(0-\infty)}, %AUC_{extrap}, t_{last}, t_{max}, \lambda_z \text{ and } t_{1/2})$ will be listed and summarized as described in Section 11.1 "General Considerations" and subsections. In addition plots of the data versus product will be provided.

The nicotine plasma concentrations will be summarized in a similar manner to the PK parameters but will also be split out by sample time-point. Geometric mean (95% CI) profiles, spaghetti plots of all subjects and individual PK profiles for each subject will also be presented.

PK parameter and plasma concentration data will also be listed along with the details of the actual times after T_0 .

TFL number	Title
TABLES	
15.2.4.5	Descriptive Statistics of Pharmacokinetic Parameters of Nicotine – PK
	Population
15.2.4.5.1	Descriptive Statistics of Pharmacokinetic Parameters of Nicotine by Sex – PK Population
15.2.4.5.2	Descriptive Statistics of Pharmacokinetic Parameters of Nicotine by
	Nicotine Level – PK Population
15.2.4.6	Descriptive Statistics of Plasma Nicotine Concentrations (ng/mL) – PK Population
15.2.4.6.1	Descriptive Statistics of Plasma Nicotine Concentrations (ng/mL) by Sex – PK Population
15.2.4.6.2	Descriptive Statistics of Plasma Nicotine Concentrations (ng/mL) by
	Nicotine Level – PK Population
FIGURES	
15.1.2.1.1	Nicotine Plasma Concentration (ng/mL) Profiles Geometric Mean
	(±95% CI) – Group-1 PK Population
15.1.2.1.2	Nicotine Plasma Concentration (ng/mL) Profiles Geometric Mean
	(±95% CI) – Group-2 PK Population
15.1.2.2.1	Nicotine Plasma Concentration (ng/mL) Profiles for All Subjects –
	Group-1 PK Population
15.1.2.2.2	Nicotine Plasma Concentration (ng/mL) Profiles for All Subjects –
	Group-2 PK Population
15.1.2.3	Nicotine Plasma Concentration (ng/mL) Profiles by Subject – PK
15124	Population
15.1.2.4	Secondary Pharmacokinetic Parameters of Nicotine – Group-1 PK
15125	Population
15.1.2.5	Pharmacokinetic Parameters of Nicotine – Group-2 PK Population

Philip Morris Products S.A. Protocol ZRHR-PK-01-EU Statistical Analysis Plan Final v 3.0 / 08 May 2014

Confidential Page 46 of 72

TFL number	Title
LISTINGS	
15.3.3.1	Listing of Pharmacokinetic Parameters of Nicotine
15.3.3.2	Listing of Plasma Nicotine Concentrations (ng/mL) and Sampling Times
15.3.3.3	Listing of Additional Pharmacokinetic Parameter Data

